#### 10.- EFFECTIVENESS ASSESSMENT

# 10.1 Primary efficacy endpoint

The primary efficacy endpoint is the change in the BACS total score throughout the trial.

The BACS scale (Brief Assessment of Cognition in Schizophrenia) was designed (Keefe et al. (2004), Spanish version Segarra et al., (2011)) to assess different aspects of cognition that tend to appear impaired in patients with schizophrenia.

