# 2.12 Objectives

Principal objective: evaluate the efficacy of vortioxetine against TAU in the treatment of cognitive impairment in newly diagnosed schizophrenia, measured by the change from baseline to week 24 (and from week 26 to week 50 in the 2nd period) in the BACS App Scale scores, using the Composite Z Score defined as the weighted sum of the patient's Individual Z Score (frame time: baseline visit, week 24, week 26 and week 50).

Secondary objective: to evaluate the efficacy of vortioxetine against TAU in the treatment of negative symptoms in newly diagnosed schizophrenia, measured by the change in the severity of negative symptoms (SANS total scores, NSA-4) from baseline. until completion (frame time: baseline visit, week 4, week 12, week 24, week 26, week 30, week 38 and week 50).

Additionally the following secondary objectives will be evaluated To assess
the efficacy of vortioxetine versus TAU in the treatment of cognitive deficits in
newly diagnosed schizophrenia, as measured by change in general
functioning (GAF total score) (frame time: baseline visit, week 12, week 24,
week 26, week 38 and week 50)

Evaluate the safety of vortioxetine in patients with newly diagnosed schizophrenia measured through the communication of any serious adverse event evaluated in relation to the Experimental Treatment (frame time: from consent signature to week 52).

 Evaluate the efficacy and reliability of the BACS App Vs BACS, measured by performing both scales and comparing results. The purpose is to confirm the reliability of the results when performing the BACS App as a faster and more practical model at the beginning and end of each period (Measurement time: baseline visit, week 24, week 26 and week 50) compared to the results obtained with the BACS scale performed at each trial visit (Measurement time: from consent signature to week 52).

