# 2.15 Primary endpoint

To assess the effectiveness of Vortioxetine vs. TAU measured by the change in Brief Assessment of Cognition in Schizophrenia (BACS App) scores

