#### 6.- STUDY DESIGN

## 6.1 Endpoints

## 6.1.1 Principal endpoint

The primary endpoint of the response consists of the improvement in cognitive functioning as assessed by the change in the BACS App Scale score: changes from baseline to week 24 (and from week 26 to week 50 in the 2nd period) in the scores of the BACS App Scale, using the Composite Z Score defined as the weighted sum of the patient's Individual Z Score (frame time: baseline visit, week 24, week 26 and week 50).

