# 9.1 Procedures per visit

The follow-up of the patients in the present study consists of 9 scheduled visits in each period (18 in total). Depending on which arm the patient falls on, the trial treatment will begin in one period or another. That is, if after the randomization of the patient, he falls into the Experimental Arm, the treatment will begin on Visit 2 (Day 1) and will end in week 24, corresponding to period 2 as the TAU treatment period. If, on the other hand, the patient falls into Control Arm, the study will begin with a first TAU period (continues with the treatment according to clinical criteria) and it will be in period 2 when the trial treatment begins (in week 26 of the study).

In this protocol the visits are arranged in chronological order, specifying the week to which each one corresponds.

The following sections detail the procedures that must be carried out at each visit.

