# 9.1.9 Visit 9: End of Treatment Visit (Week 24: day 169 ± 3 days)

- Physical examination: weight, blood pressure, heart rate, respiratory rate, temperature and abdominal perimeter
- Clinical, cognitive and functional evaluation: SAS, SANS, BACS, PANSS, GAF and NSA-4
- Dosing and dispensing treatment
- Adherence to treatment
- Review of concomitant medication
- Review of adverse events

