# 9.1.18 Visit 18: End of Study Visit (Week 52: day 379 ± 3 days)

- In the case of women of childbearing age, a urine or blood pregnancy test will be requested (the most feasible)
- Physical examination: weight, blood pressure, heart rate, respiratory rate, temperature and abdominal girth
- Blood extraction (hemogram and biochemistry)
- Clinical, cognitive and functional evaluation: BACS, PANSS and GAF
- Review of concomitant medication
- Review of adverse events

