#### The domains evaluated are:

- Verbal memory, evaluated through the word list test.
- Working memory, evaluated through the digit sequence test.
- Motor speed, assessed through the token motor test.
- Verbal fluency, assessed through the word generation test.
- Attention, evaluated through the symbol code test.
- Executive functions, assessment through the Tower of London test.

Two versions of the instrument were created in order to repeat the test avoiding the recall effect.

For correction, an overall score and scores are obtained for each of the tests included. The possible scores for each of the tests are:

- Word list test: 0-75 points.
- Digit sequence test: correct answers 0-28 points; longest sequence remembered 0-8 points.
- Token motor test\_ 0-100 points.

Symbol code test: 0-110 points.

Tower of London: 0-22 points

Administration time: 30-60 minutes.

Psychometric properties of the BACS scale:

The results showed that all tests are capable of discriminating between patients with schizophrenia and healthy subjects. In the Spanish version, the concurrent validity was similar to that reported in other languages.

Other variables of clinical improvement in terms of severity of negative symptoms are measured with the total score of SANS and NSA-4 and improvement in general functioning evaluated with changes in GAF.

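### Section 10.1 names a different primary endpoint (BACS total score, whole trial) from sections 2.12 and 6.1.1 (BACS App Composite Z, per period), and the Week-24 visit list leaves out the BACS App

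*Protocol*

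**What the plan says.** **Primary endpoint.** The synopsis (2.12) sets the principal objective as "the change from baseline to week 24 (and from week 26 to week 50 in the 2nd period) in the BACS App Scale scores". Section 6.1.1 repeats those two windows, "using the Composite Z Score defined as the weighted sum" of the patient's individual Z scores. Section 2.15 also names the App: "measured by the change in Brief Assessment of Cognition in Schizophrenia (BACS App) scores". Section 5.2.1 does too, at the start and end of each period. Section 10.1 reads: "The primary efficacy endpoint is the change in the BACS total score throughout the trial". The text that follows 10.1 describes the BACS tests by point ranges, for example "Symbol code test: 0-110 points", and mentions an overall score without defining it.

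**Statistics.** Sections 12.1 and 12.2 refer to the primary or main variable only as BACS. The detectable difference in 12.1 is 0.5 units with a standard deviation of 1.

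**Schedule.** BACS and BACS App have separate rows in the section 9 tables. At Week 52 the visit list is "Clinical, cognitive and functional evaluation: BACS, PANSS and GAF", with no App.

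**Week 24.** Section 9.1 introduces the visit lists with "The following sections detail the procedures that must be carried out at each visit". The list for Visit 9 reads "Clinical, cognitive and functional evaluation: SAS, SANS, BACS, PANSS, GAF and NSA-4". The schedule table marks the BACS App at that visit.

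**The concern.** A trial needs one primary variable, and this protocol states two. They differ in instrument, in score and in time frame. Both instruments are scheduled at baseline and Weeks 24, 26 and 50, so every completer should have data for either candidate. The trial is open-label, so leaving the choice unsettled allows it to be made after results are known.

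The time frame matters because this is a crossover. A change taken over the whole trial covers both treatments in every patient, so it does not give the per-period change on which the treatment comparison depends.

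The Week-24 omission is a separate defect affecting the same variable. Week 24 closes the period-1 change under 6.1.1. If the App is not given then, it cannot be recovered, and that patient has no within-patient App contrast. The Week-24 BACS and the period-2 App change would still be collected.

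**Working it through.** **1. The definitions side by side**

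| Section | Instrument | Score | Window |
|---|---|---|---|
| 2.12, 6.1.1 | BACS App | Composite Z | baseline to Week 24; Week 26 to Week 50 |
| 2.15 | BACS App | not stated | not stated |
| 5.2.1 | BACS App | not stated | start and end of each period |
| 10.1 | BACS | total score | throughout the trial |
| 12.1, 12.2 | BACS | units, SD 1 | by period (12.2) |

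**2. Are BACS and BACS App interchangeable here?** In the section 9 tables BACS is marked at Visits 2, 6, 9, 10, 14, 17 and 18 (7 of 18), and the App at Visits 2, 9, 10 and 17 (4 of 18). A secondary objective compares the results of the two. A protocol that tests one against the other cannot use their names interchangeably for its primary variable.

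**3. Does the sample size settle it?** Inputs from 12.1: two-sided alpha 0.05, power 80%, difference 0.5, SD 1, 15% loss.
- n = ((1.960 + 0.842) × 1 / 0.5)² = 31.4
- 31.4 / 0.85 = 36.9, rounded up to 37

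The stated 37 reproduces, with the SD of 1 acting as the SD of within-patient differences. A difference of 0.5 with SD 1 is plausible on a Z scale. It is not plausible on a raw sum of test points: the ranges given add to 75 + 28 + 100 + 110 + 22 = 335 before verbal fluency, for which no range is given. So the inputs fit 6.1.1, but 12.1 does not say so and gives no inputs for a total score.

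**4. Visit lists for the App.** The lists for Visits 2, 10 and 17 include it. The Visit 9 list does not, although the table, 2.12 and 6.1.1 place it at Week 24.

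**5. What missed Week-24 App assessments would cost.** Evaluable patients: 37 × 0.85 = 31.45, taken as 31. Paired t test on complete App pairs, difference 0.5, SD of differences 1, two-sided 5%, noncentrality 0.5 × √n:

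| App missed at Week 24 | Complete pairs | Power |
|---|---|---|
| none | 31 | 76.8% |
| 10% | 28 | 72.3% |
| 25% | 23 | 63.0% |
| 50% | 16 | 46.5% |

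The start at 77% rather than 80% arises because 12.1 uses a normal approximation. It is unrelated to this point.

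Worst case, missed in everyone: no pairs remain, and only the period-2 comparison between sequences (15 vs 16) is left for the App. If r is the between-period correlation, an SD of 1 for the differences implies an SD of change of 1/√(2(1 − r)).
- r = 0.5: SD 1.00, power 27.0%
- r = 0.3: SD 0.85, power 35.7%
- r = 0: SD 0.71, power 47.7%

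**The case against.** The strongest reply is that the intended variable can be recovered. Four sections name the App for the primary, and 6.1.1 is the full definition in the body of the protocol. A schedule footnote calls the App a version of the BACS scale, so BACS may be shorthand. The overall score in section 10 is never said to be a sum of raw points, so a standardised composite is not excluded. The phrase about the whole trial states no window; reading it as baseline to Week 52 is an inference, and the per-period analysis in 12.2 points away from it. The Week-24 omission looks clerical, since the table requires the App, and the missed-assessment rates have no basis in the document.

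Much of this stands as a limit on the claim. The score and time-frame differences depend partly on how 10.1 is read, and the power scenarios show what missing data would cost, not what this wording will cause. The instrument difference is not answered. The two forms are collected and compared separately, and a section headed as the primary efficacy endpoint names the other one. Shorthand may explain the wording, but it does not say which data set is primary.

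It is also fair to note that 2.15 and 5.2.1 do not mention the Composite Z, and that 5.2.1 brings negative symptoms into the principal objective. Correcting 10.1 alone would not fully harmonise the text.

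**Conclusion.** The point holds and must be fixed. Section 10.1 contradicts 2.12 and 6.1.1 on the primary variable, and sections 12.1 and 12.2 do not resolve it. This conflict is one of definition and rests on no assumption about numbers.

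The Week-24 omission also holds. Its size depends on how often the App is actually missed, which is unknown because the table does mark it. Power falls from about 77% to 72%, 63% or 47% if it is missed in 10%, 25% or 50% of the 31 evaluable patients. If it were missed in all of them, 27% to 48% would remain from period 2 alone. These figures assume a complete-pairs analysis, an SD of 1 for within-patient differences and, for the worst case only, a between-period correlation of 0.5 to 0.

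**What to change.** - Reword 10.1 to match 2.12 and 6.1.1: change in the BACS App Composite Z Score, baseline to Week 24 and Week 26 to Week 50.
- Name that variable in 12.1 and 12.2, and have the sponsor state which variable and score the 0.5 difference and the SD of 1 refer to.
- Add the BACS App to the Visit 9 list in 9.1.9.
- If the sponsor does intend the BACS total score, then 2.12, 2.15, 5.2.1, 6.1.1 and the sample-size inputs must change instead.

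The cost is wording only. The Week-24 App assessment is already in the schedule table, so no procedure or endpoint is added, and the 37 patients stand if the Composite Z definition is kept.

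Two side notes can be handled in the same edit and carry no weight in the verdict. The 9.1.9 list also omits the Week-24 blood draw that the table and 11.1.2 require. And 2.12 and 5.2 describe the BACS as given at every trial visit, while the tables mark 7 of 18.

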#### The domains evaluated are:

- Verbal memory, evaluated through the word list test.
- Working memory, evaluated through the digit sequence test.
- Motor speed, assessed through the token motor test.
- Verbal fluency, assessed through the word generation test.
- Attention, evaluated through the symbol code test.
- Executive functions, assessment through the Tower of London test.

Two versions of the instrument were created in order to repeat the test avoiding the recall effect.

For correction, an overall score and scores are obtained for each of the tests included. The possible scores for each of the tests are:

- Word list test: 0-75 points.
- Digit sequence test: correct answers 0-28 points; longest sequence remembered 0-8 points.
- Token motor test\_ 0-100 points.

Symbol code test: 0-110 points.

Tower of London: 0-22 points

Administration time: 30-60 minutes.

Psychometric properties of the BACS scale:

The results showed that all tests are capable of discriminating between patients with schizophrenia and healthy subjects. In the Spanish version, the concurrent validity was similar to that reported in other languages.

Other variables of clinical improvement in terms of severity of negative symptoms are measured with the total score of SANS and NSA-4 and improvement in general functioning evaluated with changes in GAF.

#### 10.2 Lab tests

Blood tests are contemplated at the initial visit and thereafter as specified in the visit schedule. Said analyzes will be carried out locally in each center, in accordance with the standards of routine clinical practice. The following tests will be carried out:

 Complete blood count including white blood cell, neutrophil, hemoglobin, and platelet counts. Blood chemistry that includes the determination of sodium, potassium, creatinine, urea, lipid profile glycemia.

#### 11.- SAFETY ASSESSMENT

# 11.1 Security Assessments

The following clinical evaluations will be performed to assess the safety profile of the trial treatment.

#### 11.1.1 Physical examination: vital signs

A physical examination and constants will be taken according to the visit schedule (section 9)

#### 11.1.2 Laboratory tests

An analytical extraction with hemogram and biochemistry will be performed that includes lipid and glycemic profile at Visit 2 (Baseline). After visit 2, patients should have another hematological and biochemical control at Visit 9, 10, 17 and 18 (Week 24, 26, 50 and 52).

#### 11.2 Definitions

#### Adverse Event (AE)

An adverse event is any unwanted medical reaction experienced by the patient at any time during the course of the study, whether or not it is considered to be related to the study treatment. This definition includes the appearance of a new disease and the exacerbation of pre-existing disorders other than the indication under study.

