# 2.14 Study indication

Recently diagnosed schizophrenia.

In the literature there is a great diversity of definitions that describe the period called "early course" of schizophrenia. Given the lack of consensual and standardized definitions, a recent review was made, reaching the conclusion that the definitions that use the duration criterion for the definition of schizophrenia of recent onset, use a range of cut-off points ranging from 1 month up to 10 years, with 1, 2 and 5 years being the most frequent. Based on this review, the 3-year inclusion criterion is adjusted to the current literature in the field of early schizophrenia.

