# 6.1.2 Secondary endpoint

Secondary endpoints consist of improvement in the severity of negative symptoms as measured by the change in severity of negative symptoms on the SANS and NSA-4 score over the visits of each period (frame time: baseline visit, week 4, week 12, week 24, week 26, week 30, week 38 and week 50).

- Additionally the following secondary objectives will be evaluated. Functional
  improvement due to the change in general functioning measured by the GAF
  scale score from the beginning to week 24 of each period (frame time:
  baseline visit, week 12, week 24, week 26, week 38 and week 50)
- Safety assessment by measuring the frequency, severity, and relationship with study medication of any adverse event described during treatment. The reasons for withdrawal and / or abandonment of the trial will also be evaluated (if applicable): from the signing of the IC until week 52.

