# 6.6 Discontinuation of study treatment and withdrawal of subjects from the study

Premature discontinuation of the clinical trial may occur due to a decision of the regulatory authorities, due to a change in the opinion of the Clinical Research Ethics Committees, due to safety and / or drug problems or indications of ineffectiveness.

It will be considered that there is a voluntary abandonment of the trial due to the refusal of the patient or legal guardian of the same to continue with the treatment or in the study, and the subject will be considered as abandonment immediately after communicating his decision to the Investigator. A patient may discontinue the trial at any time if the person, the legal representative, the investigator or the motorization committee determine that it is not in the best interest of the patient to maintain their participation.

Other reasons for discontinuation include:

- Patients with low compliance with the study drug, below 80%
- Patients requiring hospitalization for worsening psychotic disorder and / or behavioural disturbances associated with psychotic disorder.
- Patients in whom, during the study period, there is a high risk of detected suicide, according to the criteria established by Columbia University according to the risk assessment with the C-SSRS scale.
- Female patients who test positive for urine pregnancy at any time during their participation in the study.
- Any serious adverse event that recommends withdrawal at the discretion of the investigator with the agreement of the monitoring committee.
- The patient decides not to continue with the trial.
- Others: The researcher, as well as the sponsor, reserve the right to interrupt the study at any time for reasonable medical and / or administrative reasons.

Patients who drop out after randomization will not be replaced.

Patients who terminate treatment prematurely will complete an early termination interview and a safety visit.

The patient who has completed the protocol is considered to be one who has completed all the visits included in the 52-week follow-up period.

The interruption of the treatment does not imply that the case is excluded from the statistical analysis. These subjects will be part of the study and will be taken into account when analyzing the data.

There may be other circumstances for the abandonment, which in its case the researcher must make sure that the patient has abandoned the study, and will verify the causes of said abandonment.

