# Serious Adverse Event (SAE) and Serious Adverse Reaction (SAR)

AEs or ARs are considered serious that, at any dose, can cause death, threaten the life of the subject, require hospitalization of the patient or prolong an existing hospitalization, cause permanent or significant disability or disability, or give rise to an anomaly or malformation congenital. Suspicions of AE or AR that are medically important, even if they do not meet the above criteria, are also considered serious, including important medical events that require intervention to prevent one of the consequences described above from occurring. Likewise, all suspicions of transmission of an infectious agent through a drug will be reported as serious.

The concept "threatening the life of the subject" in the definition refers to the fact that, in the opinion of the researcher, the patient at the time of AE or AR is at real risk of death; It does not refer to the hypothetical AE / AR could have caused death if it had been more intense.

The concept "require hospitalization" will exclude both planned hospitalizations for scheduled treatments and those that have been planned or anticipated prior to commencing the study in relation to a pre-existing medical situation.

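### The adverse-event definition does not name worsening of schizophrenia, so an admission for psychosis put down to the illness can be missing from the AE and SAE counts that form the safety endpoint.

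*Protocol*

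**What the plan says.** Protocol 11.2 first gives a wide definition: "An adverse event is any unwanted medical reaction experienced by the patient at any time during the course of the study", whether or not the event is thought related to treatment. The next sentence sets out what this covers: "This definition includes the appearance of a new disease and the exacerbation of pre-existing disorders other than the indication under study". Section 2.14 gives the indication: "Recently diagnosed schizophrenia".

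The seriousness definition in 11.2 applies to events already classed as adverse events or reactions: "AEs or ARs are considered serious that, at any dose, can cause death, threaten the life of the subject, require hospitalization of the patient". The only admissions it leaves out are those planned or foreseen before the study.

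Section 6.6 lists among the reasons for discontinuation "Patients requiring hospitalization for worsening psychotic disorder and / or behavioural disturbances associated with psychotic disorder". A separate item in the same list is "Any serious adverse event that recommends withdrawal at the discretion of the investigator with the agreement of the monitoring committee". Nothing links the two, and nothing in 6.6 refers the psychosis admission to section 11.

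Section 6.1.2 builds the safety endpoint on adverse events: "Safety assessment by measuring the frequency, severity, and relationship with study medication of any adverse event described during treatment". The same bullet adds that the grounds for leaving the trial will be assessed. The safety objective (2.12 and 5.2.2) is measured through serious adverse events.

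**The concern.** The trial adds vortioxetine to antipsychotic treatment in clinically stable patients who enter with few positive symptoms (2.16 and 7.1). A reader of the safety results will want psychotic destabilisation compared between vortioxetine and TAU. The definition leaves the status of exactly that event open. It can be settled case by case, by an investigator who knows the treatment because the trial is open-label (6.4).

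Setting the indication apart can be defended when its worsening is captured as an efficacy outcome. Here the efficacy endpoints are cognition (BACS and BACS App), negative symptoms (SANS and NSA-4) and functioning (GAF). None measures positive symptoms or relapse. If psychotic admissions are missing from the AE and SAE tables as well, the comparison of a key harm is incomplete.

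**Working it through.** No arithmetic is needed for the defect, which lies in how the definitions connect. Take one event: an unplanned admission for psychotic worsening.

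1. **Discontinuation.** 6.6 names it, with no limit to arm or period.
2. **Is it an AE?** The opening sentence of the AE definition could take it in. The scope sentence names exacerbations only of disorders apart from the indication, which is schizophrenia (2.14). The event is therefore not named as an AE, and the wording suggests that it was meant to be left out.
3. **Is it an adverse reaction?** That definition makes no exception for the indication, but it requires a reaction to an investigational drug. The causality criteria in 11.2 class an event as related only if factors such as the patient's clinical state do not explain it. In a patient with schizophrenia that explanation is usually at hand.
4. **Is it serious?** An unplanned admission meets the hospitalisation criterion, but the test applies only to what has passed step 2 or step 3.
5. **Is it collected?** 11.4 describes systematic collection of related events only. The opening of 11.5 limits reporting to serious events that are related and unexpected, although a later sentence there speaks of serious adverse events in general.

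The outcome by situation:

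| Admission for psychotic worsening | Named in the AE definition | Adverse-reaction route | Visible as a withdrawal reason |
|---|---|---|---|
| On vortioxetine, attributed to the drug | No | Yes, and serious through hospitalisation | Yes |
| On vortioxetine, attributed to the illness | No | No | Yes |
| On TAU | No | Not available | Yes |

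The same event can thus be counted or not according to attribution, and attribution can bring it in under one treatment only.

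**Scheduled measurement of positive symptoms.** The visit tables in section 9 mark PANSS at visits 1, 9, 10, 17 and 18, that is, at screening and weeks 24, 26, 50 and 52. No PANSS is scheduled between the start and week 24, or between weeks 26 and 50 (50 − 26 = 24 weeks). Scheduled assessments would therefore not show worsening within a period. An unscheduled visit could.

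**The case against.** The strongest reply is that the text excludes nothing outright. The first sentence of the AE definition is wide, the second says what is included without saying that the list is closed, and an investigator could properly record a psychotic exacerbation as an AE. This stands. The defect is ambiguity, not prohibition, and a reader who infers that such events can never be AEs goes beyond the text. Ambiguity still permits uneven recording by people who know the treatment.

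A second reply is that the event is not lost. 9.1.19 calls for a prompt decision on an unscheduled visit when clinical status changes markedly, and that visit includes PANSS. Medical history is marked at every visit. Patients who stop early have a safety visit (6.6), and the main reason for withdrawal is recorded (7.3.4). The 6.1.2 bullet has withdrawal reasons assessed. All of this stands. It rules out two tempting inferences: that AE reporting is the only way worsening can be seen, and that the admission vanishes from 6.1.2 altogether. None of these routes makes it an AE or SAE count.

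A reader might also infer a bias towards finding no excess on vortioxetine. The documents do not show this. The qualifier applies in both periods, and the one way back in, through attribution, exists only on vortioxetine, so uneven counting could equally add events there.

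Nor does 6.6 show that the protocol regards the admission as a safety risk. It gives no rationale, and the safety criteria in 7.3.2 do not name it.

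Finally, it can be said that the related-only wording of 11.4 is the larger barrier. It is a second barrier: widening 11.4 to all AEs would still leave open whether this event is one. Both have to change.

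**Conclusion.** The point holds as a gap in a stated definition. Psychotic worsening, including an admission that 6.6 makes a reason to discontinue, need not be recorded as an AE or tested for seriousness unless it is attributed to vortioxetine. It can therefore be missing from, or inconsistently entered in, the AE and SAE frequencies behind the safety objective and endpoint, although it may appear as a withdrawal reason or at an unscheduled visit.

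The size cannot be given in events. The protocol states no relapse or admission rate, so a claim that these would be most of the trial's serious events has no basis in the documents. The direction of any bias is likewise uncertain.

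The conclusion rests on reading the scope sentence as leaving the indication out, which is its natural sense, and on the absence of any other provision in the protocol that gives a psychosis admission AE or SAE status.

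**What to change.** Reconcile 6.6, the AE and SAE definitions in 11.2, 11.4 and 11.5. Two changes are needed together.

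- In 11.2, delete the qualifier that sets the indication apart, or add a sentence such as: *Worsening of psychotic symptoms beyond the baseline state, and any hospitalisation for it, is recorded as an AE, and as an SAE where a seriousness criterion is met, in both periods and regardless of attribution.* Refer the hospitalisation item in 6.6 to section 11.5.
- In 11.4 and 11.5, align the wording that restricts collection and reporting to related events, so that these events are actually captured. Changing 11.2 alone would leave an unrelated admission uncollected.

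The cost is a short text change in these sections, a matching case report form instruction, and a few more AE and SAE forms in both periods. No visit or test is added, and no treatment or stopping rule changes. The change should be made before patients are enrolled, because events not recorded when they occur may not be reliably recoverable later.
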